#### **4.8.5 Interim Analyses**

No formal schedule of interim analyses is planned. Reports of adverse events from this study may be reviewed and summarized periodically while the study is ongoing to ensure the safety of subjects.

#### **4.8.6 PK/PD Analyses**

Optional Serum and/or plasma samples collected for PK/PD analysis will be analyzed for biomarkers including but not limited to isoforms of VEGF and ranibizumab. The samples will be stored at either Retina Consultants of Houston or Genentech after the testing. Residual serum and plasma remaining once the primary analyses are completed may be used for

further exploratory analyses of VEGF and other systemic biomarkers related to angiogenesis, atherosclerosis, and inflammation.

#### **4.9 DATA QUALITY ASSURANCE**

Accurate, consistent, and reliable data will be ensured through the use of standard practices and procedures.

### **5. ASSESSMENT OF SAFETY**

#### **Specification of Safety Variables**

Safety assessments will consist of monitoring, reporting adverse events (AEs) and serious adverse events (SAEs) that are considered related to {study drug}, all events of death, and any study specific issue of concern.

#### **5.1 ADVERSE EVENTS**

An AE is any unfavorable and unintended sign, symptom, or disease temporally associated with the use of an investigational medicinal product (IMP) or other protocol-imposed intervention, regardless of attribution. AE's will be recorded from screen through week 156.

This includes the following:

- AEs not previously observed in the subject that emerge during the protocol-specified AE reporting period, including signs or symptoms associated with AMD that were not present prior to the AE reporting period.
- Complications that occur as a result of protocol-mandated interventions (e.g., invasive procedures such as cardiac catheterizations).

If applicable, AEs that occur prior to assignment of study treatment associated with medication washout, no treatment run-in, or other protocol-mandated intervention.

Preexisting medical conditions (other than the condition being studied) judged by the investigator to have worsened in severity or frequency or changed in character during the protocol-specified AE reporting period.

#### **5.2 METHODS AND TIMING FOR ASSESSING AND RECORDING SAFETY VARIABLES**

The investigator is responsible for ensuring that all AEs and SAEs that are observed or reported during the study are collected and reported to the FDA, appropriate IRB(s), and Genentech, Inc. in accordance with CFR 312.32 (IND Safety Reports).

##### **5.2.1 Adverse Event Reporting Period**

The study period during which all AEs and SAEs must be reported begins after informed consent is obtained and initiation of study treatment or "initiation of any non-standard of care study procedures" and ends 30 days

following the last administration of study treatment or study discontinuation/termination, whichever is earlier. After this period, investigators should only report SAEs that are attributed to prior study treatment.

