#### **4.8.2 Safety Analyses**

Any adverse events, laboratory assessments, physical examinations, vital signs, ocular examinations and measurements from all 60 subjects will be utilized to summarize safety data for this study.

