#### 5.5.2.6 Post-Study Adverse Events

The investigator should expeditiously report any SAE occurring after a subject has completed or discontinued study participation if attributed to prior {study drug} exposure. If the investigator should become aware of the development of cancer or a congenital anomaly in a subsequently conceived offspring of a female subject who participated in the study, this should be reported as an SAE.

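### Section 5.2.1 closes AE/SAE reporting no later than 30 days after the last injection, while Sections 5.1 and 5.2 run it to week 156; in the PRN year, sites could collect safety data under different rules

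*Combined protocol and SAP*

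**What the plan says.** All references are to the combined protocol and SAP.

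- **Section 5.2.1** sets the period in which all AEs and SAEs must be reported. It ends 30 days "following the last administration of study treatment or study discontinuation/termination, whichever is earlier". It then adds: "After this period, investigators should only report SAEs that are attributed to prior study treatment".
- **Section 5.1** states that "AE's will be recorded from screen through week 156". Among the events it covers are "AEs not previously observed in the subject that emerge during the protocol-specified AE reporting period".
- **Section 5.2** makes the investigator responsible for ensuring that "all AEs and SAEs that are observed or reported during the study are collected and reported to the FDA", the IRBs and the drug manufacturer.
- **Section 4.5.1 and the Appendix A schedules** have AEs reviewed at every visit, including all 13 year-3 visits from week 108 to week 156.
- **Section 5.6.2** requires SAEs to be sent to the manufacturer, including those judged unrelated, and non-serious AEs to be forwarded quarterly. It names no cut-off tied to the last injection.
- **Sections 3.2 and 3.3** make year 3 a PRN phase for Cohort A and for Cohort B subjects who are dry at 12 weeks. A stated purpose is to learn whether subjects stay dry without further injections.
- **Section 4.8.3** lists incidence and severity of AEs as a secondary outcome. **Section 4.8.1** places the complete-data analysis at week 156.

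**The concern.** A reporting window that ends 30 days after the last dose does little harm when dosing continues to the end of follow-up. In this trial dosing may stop well before then. Subjects who do well in year 3 may receive no further injection, yet they are seen monthly to week 156. Under Section 5.2.1 their reporting period may close around week 104; under Sections 5.1 and 5.2 it stays open for another year.

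Take a stroke at month 30, judged unrelated, in a subject not injected since week 100. Section 5.5.2.8 lists stroke as an event of special interest, and Section 5.6.2 sends such events to the manufacturer whatever their cause. Section 5.2.1 would not have it reported.

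At stake is the comparability of year-3 AE counts across about 4 sites (Section 4.1.1). A site following Section 5.2.1 could stop reporting non-serious AEs and unrelated SAEs; a site following Section 5.1 would continue.

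**Working it through.** The plan states no figure to reproduce. The check is calendar arithmetic followed by a comparison of the sections.

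**Step 1: when the period closes.** Let L be the day of the last injection and D the day of discontinuation or termination, with L ≤ D. The earlier-of rule can be read as min(L + 30, D) or as min(L + 30, D + 30). Either way the end is no later than L + 30.

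**Step 2: inputs.**
- Follow-up runs to week 156 in both cohorts (Section 3.2), so the end is day 7 × 156 = 1092.
- Year-3 visits are weeks 108, 112, …, 156, which is 13 visits on days 756 to 1092 (Appendix A).
- Cohort A's last fixed injection is at week 100 (Sections 3.2 and 4.2). Section 2 speaks of monthly injections for 104 weeks, so week 104 is shown as an alternative.

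**Step 3: uncovered follow-up.** For a last injection at week k, the cut-off is day 7k + 30 and the uncovered time is max(0, 1092 − (7k + 30)) = max(0, 1062 − 7k).

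| Last injection (week k) | Cut-off day | Days uncovered | Year-3 visits after cut-off |
|---|---|---|---|
| 100 | 730 | 362 | 13 of 13 |
| 104 | 758 | 334 | 12 of 13 |
| 128 | 926 | 166 | 6 of 13 |
| 148 | 1066 | 26 | 1 of 13 |
| 152 | 1094 | 0 | 0 of 13 |

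The first row is 362 of the 364 days between weeks 104 and 156. If day 1095 (the hard-endpoint day) is used for week 156, each non-zero figure rises by 3 days and the last row becomes 1 day.

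**Step 4: Cohort B.** A subject who reaches the 12-week interval in year 3 is not injected at that visit (Section 3.2). PRN therefore begins 84 days after the last injection, which is 84 − 30 = 54 days past the cut-off (47 to 61 with the ±7-day window). A subject at 12 weeks by week 104, last injected at week 92 and never re-treated, has cut-off day 674. That leaves 1092 − 674 = 418 days uncovered, of which 728 − 674 = 54 precede week 104.

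**Step 5: which sections conflict.**
- *Direct conflict:* 5.2.1 against 5.1 (end point) and against 5.2 (all events during the study collected and reported).
- *Tension:* 4.5.1 and Appendix A review AEs at visits that 5.2.1 may place outside the period. Section 5.6.2 has unrelated SAEs sent on without such a limit.
- *Linked wording:* 5.5.2.2 ties death reporting to the same period but cites a Section 5.1.2 that does not exist. The opening of Section 5 limits AE and SAE reporting to related events plus all deaths.

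**The case against.** **Recording is not reporting.** Section 5.1 speaks of recording and 5.2.1 of reporting, and reporting elsewhere means onward reporting to the FDA, IRBs and manufacturer. On that view the secondary outcome is safe, because AEs are reviewed at every visit and Section 4.8.2 says that "measurements from all 60 subjects will be utilized to summarize safety data for this study". Part of this stands: the AE outcome does not depend on 5.2.1 alone. It does not remove the conflict, because 5.1 itself refers to events arising in the AE reporting period and 5.2 requires both collection and reporting.

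**The cut-off cannot be applied going forward.** The last PRN injection is known only in retrospect, so a site must either guess that none will follow or discard events later. No section instructs either. This stands, and it is why the consequence is worded as something a site could do.

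**Not every nearby section contradicts 5.2.1.** This also stands.
- Section 4.8.2 sets no time window.
- The early-termination visit in 4.5.2, at 28 ± 7 days, can ask about events without changing which ones count.
- Section 5.5.2.6 requires reporting of "any SAE occurring after a subject has completed or discontinued study participation if attributed to prior" exposure, which is compatible with 5.2.1.
- The start dates look different, since 5.2.1 "begins after informed consent is obtained and initiation of study treatment or" the start of procedures outside standard care. That second branch can fall at screening after consent, so the difference mostly disappears.

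**Stronger readings.** A reader might infer that year-3 events will be lost, or that the AE comparison between arms is biased. The documents support neither: several sections call for full collection, and no re-treatment frequency is given from which to size or sign a difference between arms.

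**Conclusion.** The point holds as an internal inconsistency in the end of the AE/SAE reporting period. The possible gap depends on the date of the last injection. It is 0 days at week 152 and 362 days, nearly all of year 3, for a Cohort A subject last injected at week 100.

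The large values are per-subject extremes. They assume a site that applies 5.2.1 literally, no PRN injection after the stated week, and nominal visit days. They are not an estimate of expected loss, and none can be made from the documents. The supportable conclusion is that year-3 AE data could be gathered under different rules at different sites. That warrants a wording change; it does not show that the safety outcome has failed.

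**What to change.** Reconcile 5.2.1 with 5.1 and 5.2 by stating one period for all AEs, SAEs and deaths, regardless of attribution. It starts at screening, after informed consent, and ends at the **later** of:

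(a) the week 156 visit or, for a subject who withdraws, the early-termination visit or the date of discontinuation; and
(b) 30 days after the last injection.

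After that, SAEs attributed to prior study treatment are still reported, as 5.2.1 and 5.5.2.6 already require.

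Both limbs are needed. The early-termination visit can fall on day 28 − 7 = 21 after the last injection, so ending there alone would give less cover than the present 30 days. Naming the date of discontinuation supplies an end point for subjects who miss that visit.

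Align the opening of Section 5, Section 5.1 and Section 5.5.2.2 with this period, and change the 5.1.2 cross-reference in Section 5.5.2.2 to 5.2.1.

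The cost is a protocol wording change, slightly more AE reporting in year 3, and a brief follow-up contact for subjects whose 30 days run past their last visit. For completers, these are subjects injected after day 1092 − 30 = 1062; a week-152 injection runs to day 1094. No other visits are added, because AEs are already reviewed at each one.

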### **5.2.2 Assessment of Adverse Events**

All AEs and SAEs whether volunteered by the subject, discovered by study personnel during questioning, or detected through physical examination, laboratory test, or other means will be reported appropriately. Each reported AE or SAE will be described by its duration (e.g., start and end dates), regulatory seriousness criteria if applicable, suspected relationship to ranibizumab (see following guidance), and actions taken.

## **5.3 EVALUATIONS**

Ophthalmologic evaluations will include slit lamp examination, dilated binocular indirect high-magnification ophthalmoscopy, measurements of BCVA, and intraocular pressure pre- and post dose. (See Section 4.5 for a detailed description of the study assessments.)

## **5.4 VITAL SIGNS**

Pulse and blood pressure will be measured at protocol-specified study visits (see Section 4.5).

## **5.5 PROCEDURES FOR ELICITING, RECORDING, AND REPORTING ADVERSE EVENTS**

### **5.5.1 Eliciting Adverse Events**

A consistent methodology for eliciting AEs at all subject evaluation time points should be adopted. Examples of non-directive questions include:

- “How have you felt since your last clinical visit?”
- “Have you had any new or changed health problems since you were last here?”

### **5.5.2 Specific Instructions for Recording Adverse Events**

Investigators should use correct medical terminology/concepts when reporting AEs or SAEs. Avoid colloquialisms and abbreviations.

#### **5.5.2.1 Diagnosis vs. Signs and Symptoms**

If known at the time of reporting, a diagnosis should be reported rather than individual signs and symptoms (e.g., record only liver failure or hepatitis rather than jaundice, asterixis, and elevated transaminases). However, if a constellation of signs and/or symptoms cannot be medically characterized as a single diagnosis or syndrome at the time of reporting, it is ok to report the information that is currently available. If a diagnosis is subsequently established, it should be reported as follow-up information.

### **5.5.2.2 Deaths**

All deaths that occur during the protocol-specified AE reporting period (see Section 5.1.2), regardless of attribution, will be reported to the appropriate parties. When recording a death, the event or condition that caused or contributed to the fatal outcome should be reported as the single medical concept. If the cause of death is unknown and cannot be ascertained at the time of reporting, report "Unexplained Death".

### **5.5.2.3 Preexisting Medical Conditions**

A preexisting medical condition is one that is present at the start of the study. Such conditions should be reported as medical and surgical history. A preexisting medical condition should be re-assessed throughout the trial and reported as an AE or SAE only if the frequency, severity, or character of the condition worsens during the study. When reporting such events, it is important to convey the concept that the preexisting condition has changed by including applicable descriptors (e.g., "more frequent headaches").

### **5.5.2.4 Hospitalizations for Medical or Surgical Procedures**

Any AE that results in hospitalization or prolonged hospitalization should be documented and reported as an SAE. If a subject is hospitalized to undergo a medical or surgical procedure as a result of an AE, the event responsible for the procedure, not the procedure itself, should be reported as the SAE. For example, if a subject is hospitalized to undergo coronary bypass surgery, record the heart condition that necessitated the bypass as the SAE.

Hospitalizations for the following reasons do not require reporting:

- Hospitalization or prolonged hospitalization for diagnostic or elective surgical procedures for preexisting conditions
- Hospitalization or prolonged hospitalization required to allow efficacy measurement for the study or
- Hospitalization or prolonged hospitalization for scheduled therapy of the target disease of the study.

### **5.5.2.5 Pregnancy**

If a female subject becomes pregnant while receiving investigational therapy or within 90 days after the last dose of study drug, a report should be completed and expeditiously submitted to the Genentech, Inc. Follow-up to obtain the outcome of the pregnancy should also occur. Abortion, whether accidental, therapeutic, or spontaneous, should always be classified as serious, and expeditiously reported as an SAE. Similarly, any congenital anomaly/birth defect in a child born to a female subject exposed to the {study drug} should be reported as an SAE.

#### 5.5.2.6 Post-Study Adverse Events

The investigator should expeditiously report any SAE occurring after a subject has completed or discontinued study participation if attributed to prior {study drug} exposure. If the investigator should become aware of the development of cancer or a congenital anomaly in a subsequently conceived offspring of a female subject who participated in the study, this should be reported as an SAE.

#### 5.5.2.7 Reconciliation

The Sponsor agrees to conduct reconciliation for the product. Genentech and the Sponsor will agree to the reconciliation periodicity and format, but agree at minimum to exchange monthly line listings of cases received by the other party. If discrepancies are identified, the Sponsor and Genentech will cooperate in resolving the discrepancies. The responsible individuals for each party shall handle the matter on a case-by-case basis until satisfactory resolution.

#### 5.5.2.8 AEs of Special Interest (AESIs)

AEs of Special Interest are defined as a potential safety problem, identified as a result of safety monitoring of the investigational product.

The ranibizumab Events of Special Interest are:

- Retinal pigment epithelial tear
- Increased intraocular pressure > 30 mmHg not responsive to maximal topical IOP-lowering drugs measured on two separate days
- Traumatic cataract
- Endophthalmitis
- Intraocular inflammation of > 2+ cell (including vitritis and uveitis)
- Retinal detachment
- ATEs, including stroke

#### 5.5.2.9 Evaluation of Causality

To ensure consistency of AE and SAE causality assessments, investigators should apply the following general guideline:

- **Yes** – There is plausible temporal relationship between the onset of the AE and administration of the ranibizumab and the AE cannot be readily explained by the subject's clinical state, intercurrent illness, or concomitant therapies; and/or the AE follows a known pattern of response to the ranibizumab; and/or the AE abates or resolves upon discontinuation of the ranibizumab or dose reduction, if applicable, reappears upon re-challenge.
- **No** – Evidence exists that the AE has an etiology other than the ranibizumab (e.g. preexisting medical condition, underlying disease, intercurrent illness, or concomitant medication); and/or the AE has no plausible temporal relationship to ranibizumab administration (e.g. cancer diagnosed 2 days after first dose of study drug).

Expected adverse events are those adverse events that are listed or characterized in the Package Insert or current Investigator Brochure.

Unexpected adverse events are those not listed in the Package Insert (P.I.) or current Investigator Brochure (I.B.) or not identified. This includes adverse events for which the specificity or severity is not consistent with the description in the P.I. or I.B. For example, under this definition, hepatic necrosis would be unexpected if the P.I. or I.B. only referred to elevated hepatic enzymes or hepatitis.

#### 5.5.2.10 Evaluation of Severity

The severity of an AE will be graded by the investigator using a 3-point scale (mild, moderate, or severe).

- **Mild** – dose not interfered in a significant manner with subject's normal functioning level. It may be an annoyance. Prescription drugs are not ordinarily needed for relief of symptoms, but may be given because of the personality of the subject.
- **Moderate** – produces some impairment of functioning but is not hazardous to health. It is uncomfortable or an embarrassment. Treatment for symptom (including prescription drugs) may be needed.
- **Severe** – Produces significant impairment of the functioning or incapacitation and is a definite hazard to the subject's health. Treatment for symptom may be given and/or subject is hospitalized.

### 5.6 SERIOUS ADVERSE EVENTS

An AE should be classified as an SAE if the following criteria are met:

- It results in **death** (e.g., the AE actually causes or leads to death).
- It is **life threatening** (e.g., the AE, in the view of the investigator, places the subject at immediate risk of death. It does not include an AE that, had it occurred in a more severe form, might have caused death.).
- It requires or prolongs **inpatient hospitalization**. Inpatient hospitalization is defined as admission to a hospital or emergency room for longer than 24 hours. Prolongation of existing hospitalization is defined as hospital stay that is longer than was originally anticipated for the event, or is prolonged due to the development of a new AE as determined by the investigator or treating physician.
- It results in persistent or significant **disability/incapacity** (e.g., the AE results in substantial disruption of the subject's ability to conduct normal life functions).
- It results in a **congenital anomaly/birth defect** in a neonate/infant born to a mother exposed to the IMP.
- It is considered a **significant medical event** by the investigator based on medical judgment. May not be immediately life-threatening or result in death or hospitalization, but may jeopardize the subject or may require medical/surgical intervention to prevent one of the outcomes listed above.

### **5.6.1 Criteria for Serious Sight-Threatening Ocular Adverse Events :**

- Adverse event causes a decrease in BCVA of > 30 letters (compared with the most recent assessment of BCVA) lasting > 1 hour
- Adverse event causes a decrease in VA to the level of light perception or worse
- Adverse event requires surgical intervention (e.g., conventional surgery, vitreous tap or biopsy with intravitreal injection of anti-infectives, or laser or retinal cryopexy with gas) to prevent permanent loss of sight
- Adverse event is associated with severe intraocular inflammation (ie, 4+ anterior chamber cell/flare or 4+ vitritis)
- In the opinion of the investigator, AE may require medical intervention to prevent permanent loss of sight

### **5.6.2 SAE Reporting**

Investigators must report all SAEs to Genentech within the timelines described below. The completed Medwatch/case report should be faxed immediately upon completion to Genentech Drug Safety at:

[contact]

OR

[contact]

- Relevant follow-up information should be submitted to Genentech Drug Safety as soon as it becomes available.
- Serious AE reports that are related to the 0.5 mg ranibizumab and AEs of Special Interest (regardless of causality) will be transmitted to Genentech within fifteen (15) calendar days of the Awareness Date.
- Serious AE reports that are unrelated to the 0.5 mg ranibizumab will be transmitted to Genentech within thirty (30) calendar days of the Awareness Date.

Additional Reporting Requirements to Genentech include the following:

- Any reports of pregnancy following the start of administration with the 0.5 mg ranibizumab and will be transmitted to Genentech within thirty (30) calendar days of the Awareness Date.
- All Non-serious Adverse Events originating from the Study will be forwarded in a quarterly report to Genentech.

